#### **2.5.4 Safety Analysis Set**

The Safety Analysis Set will include all participants from the As Treated Population who provided safety data.

It is assumed that all participants applying VIBLOK at least once are included in the safety analysis; if that is not so, an explanation will be provided.

#### **2.6 Multiplicity**

The primary endpoint for this clinical study is SADE incidence during minimally 26 days of VIBLOK use in the As Treated Population. This analysis will be repeated for the Per Protocol Population. Since the primary endpoint is a safety endpoint and all other statistical analyses are secondary endpoints no correction for multiplicity will be performed to prevent alpha inflation.

#### **2.7 Interim Analysis**

A Data Safety Monitoring Committee is established for this study. The aim of the DMC is to protect and serve the VIBLOK SAFE Trial participants, specifically regarding safety, and to assist and advise the Study Sponsor and the Study Steering Committee so as to protect the validity and credibility of the trial. Full details can be found in the DMC Charter.

No adjustments for the Type I error will be made.

#### **2.8 General Issues For Statistical Analyses**

Descriptive statistics (N, Mean, Median, STD, min, Max) will be presented for continuous data, frequencies and percentages will be presented for categorical variables. Continuous, non-normally distributed variables will be analyzed using the nonparametric Wilcoxon signed-rank (within group comparisons) test or Wilcoxon rank-sum test (between group comparisons). The latter will be accompanied by Hodges-Lehmann estimates (point estimate and 95% exact confidence interval) to assess the location of the shift between groups. Twosided exact 95% Clopper-Pearson confidence intervals will be calculated for categorical variables. Hypotheses will be tested two-sided using an alpha-level of 5%.

#### **2.9 Data Handling Rules/Derived and Computed Variables**

The handling of drop-outs and incomplete data (like diaries etc.) will be described in the Data Handling and Presentation Plan.

### **3. Study Participants Information**

#### **3.1 Participant Disposition**

The number of participants who entered and completed each phase of the study will be provided, as well as the reasons for all discontinuations, grouped by major reason:

- Lost to follow-up
- Participant requested withdrawal from the study
- Participant withdrew consent
- Relocated to another geographic location
- Other
- Investigator withdrew participant from the study
- Investigator deems medically necessary
- Failure to maintain adequate study compliance
- Inclusion/exclusion criteria not met
- Other
- Other reason.

A flow chart will be included (see Annex I).

There will also be a listing of all participants discontinued from the study after enrollment, broken down by center, giving a participant identifier, the specific reason for discontinuation, and the duration of applying VIBLOK before discontinuation. Refer to Annex II.

Three attempts will be made to contact the participant in case of lost to follow-up. The method of the attempt (phone, written, e-mail, other) will be presented.

### **3.2 Protocol Deviations**

All important deviations related to study inclusion or exclusion criteria, conduct of the study, participant management or participant assessment will be presented.

Protocol deviations will be summarized by center and grouped into different categories:

- Informed consent not signed and/or dated
- Wrong version of the informed consent used
- Inclusion / exclusion criteria
- Missed visits
- Visit not within window
- Protocol required data collection / testing
- Other deviation

The reason for the deviation, including the root cause, will be summarized by center using the following categories:

- Medical justification
- Participant non-compliance
- Study center error / non-compliance
- Other reason

Whether or not corrective action was needed will be summarized by center.

Individual participants with protocol deviations will be listed, including the description of the deviation, broken down by center.

### 3.3 Data Sets Analyzed

The frequencies and percentages of participants in each analysis set will be presented. A tabular listing of all participants, visits and observations excluded from the analysis sets will be provided (see Annex III for an example).

### 3.4 Demographics and Other Baseline Characteristics

The critical demographic and baseline characteristics of the participants, as well as other factors arising during the study that could affect response, will be displayed by use of tables. The data for the All Enrolled Set will be given first followed by data on the As Treated Population, Per Protocol Population and Safety Analysis Set.

The variables, assessed at the screening visit and at Visit 1, displayed will include:

- demographic variables
  - Age (years)
  - Gender (Male / Female)
  - Race/Ethnic Origin (Participant chose not to share this data / African, American or Black / Asian / Caucasian / Hispanic or Latina / Other race/ethnic origin)
- HSV Serology
  - Units HSV-2 IgG antibody (aU/ml)
  - Units HSV-2 IgG antibody (Negative / Positive / Borderline)
  - Units HSV-1 IgG antibody (aU/ml)
  - Units HSV-1 IgG antibody (Negative / Positive / Borderline)
  - Units HSV- IgM antibody (Negative / Positive / Borderline)
  - Overall result of the Western blot or Allegria Essay test (HSV2 positive and HSV1 negative / HSV2 positive and HSV1 positive / HSV2 negative and HSV1 positive / HSV2 negative and HSV1 negative / HSV positive but origin HSV1 or HSV2 unclear)
- Anti-Viral therapy
  - Current use of any anti-viral therapy at screening (Yes / No)
  - Did the participant stop with any anti-viral therapy recently at screening? (Yes / No)
  - Has anti-Viral therapy been stopped at least 7 days ago at Visit 1? (Yes / No (delay visit 1 or withdraw participant))
- Medical History (general)
  - Does the participant have hypertension? (No/Controlled / Uncontrolled)
  - Does the participant diabetes? (No/ Type 1 / Type 2)
  - Does the participant have cardiac disease? (Yes / No)
  - Is the participant HIV positive? (Yes / No / Unknown)
  - Does the participant have any known allergies? (No / Hay Fever, Dust Mites or Animal Dander / Contact Allergy / (Household) Chemicals / Perfume or Body care products / Latex / Other)
  - Does the participant have a significant autoimmune disease? (No/ Multiple Sclerosis / Myasthenia Gravis / Crohn Disease / Colitis Ulcerosa / Psoriasis / Vitiligo / Lupus Erythematosus / Rheumatoid arthritis /Other)

- Does the participant have any other for the study relevant medical condition? (Yes / No / Unknown)
- Have there been any changes in medical history since previous visit? (Yes / No)

At visit 1 the actual medical history status will be presented, i.e. the data from the screening visit including the changes reported at Visit 1.

- History of genital herpes

- Years since first date of diagnosis of genital herpes
- How was the diagnosis "genital herpes" made (Clinical / Culture or PCR / Blood test)
- Type of blood test performed (Alegria assay / UW Western blot / Other )
- The number of recurrences of genital herpes the participant had in the past year ( today –1y)
- Years since last recurrence the participant had
- Did the participant experience HSV recurrence at Visit 1 since the screening visit? (No / Yes)

- Targeted Physical Exam - General

- Height (cm)
- Weight (kg)
- Heart rate (bpm)
- Systolic and diastolic Blood pressure (mmHg)
- Genital
- Any (new) abnormalities in the inguinal and/or pubis area related to genital herpes? (Yes / No)
- Any (new) abnormalities in the peri-anal area related to genital herpes? (Yes / No)
- Any (new) abnormalities in the genital area related to genital herpes? (Yes / No)
- Any (new) obvious discharge present in the genital, peri-anal, inguinal or pubis area? (Yes / No)
- Any (new) other abnormalities in the genital, peri-anal, inguinal or pubis area, NOT related to genital herpes but relevant for the study (at the judgement of the investigator)? (Yes / No)

At visit 1 the actual targeted Genital Exam will be presented, i.e. the data from the screening visit including the new abnormalities reported at Visit 1.

- Grooming Habits

- Genital grooming habits (None / Shaving / Waxing / Other)
- Frequency of performing these extra genital grooming habits (Daily / Weekly / Monthly / Other)
- Did participant change any genital grooming since the screening visit? (Yes / No)

At visit 1 the actual grooming habits will be presented, i.e. the data from the screening visit including the changes reported at Visit 1.

- Medication vs Treatment

- Any use of medication, topical cream or other product on a continuous basis, for the treatment or maintenance of genital herpes or any other medical condition as mentioned in the medical history? (Yes / No)
- Treatment in case of an outbreak of genital herpes to alleviate/ treat the genital herpes on top of any treatment/maintenance of genital herpes on a continuous basis (No additional treatment / Prescription medication /

Nonprescription medication / (Topical) cream / Any other treatment). More than one answer allowed.

- Are there any changes in medication, topical cream or any other product to alleviate genital herpes since screening visit? (Yes / No)
- Pregnancy test (female only)
  - Did the participant perform a urine pregnancy test at screening visit? (Yes, pregnant / Yes, not pregnant / No, pregnancy test to be performed at visit 1 at the latest / No, participant is not of child bearing potential)
  - Has a urine pregnancy test been performed at visit 1? (Not applicable, pregnancy test performed during screening visit / Yes, pregnant withdraw participant from study / Yes, not pregnant / No, complete a protocol deviation and withdraw participant from study)
- Instructions of use
  - Has the participant been instructed to take the swab(s)?
  - Has participant been instructed to store the swabs correctly?
  - Has participant been instructed to apply the VIBLOK correctly?
  - Has the participant been instructed to complete the diary correctly?
  - Has the participant been instructed to complete the swab log(s) correctly?
  - Has the participant been instructed what to do in case of genital herpes outbreak?

Possible answers to the questions are:

- No
- Yes, speed of the participant to perform task correctly is fast
- Yes, speed of the participant to perform task correctly is medium - Yes, speed of the participant to perform task correctly is slow

In addition to tables giving group data for these baseline variables, relevant individual participant demographic and baseline data, and all concomitant medication for all individual participants enrolled (broken down by center) will be presented in by-participant tabular listings.

### 3.5 Measurements of Treatment Compliance

Frequencies and percentages will be presented of whether or not the participant did return all used and unused Viblok packages at Visit 2 and 3.

### 3.6 Post Visit 1 data

The critical characteristics of the participants, as well as other factors arising during the study and collected after Visit 1 that could affect response, will be displayed by use of tables. The data for the As Treated Population will be given first followed by data on the Per Protocol Population.

The variables displayed will include:

- Administrative information
  - FU call performed (Yes / No)
- Verification study procedures
  - Did the participant have full understanding and no remaining questions with respect to the swabbing procedures? (Yes / No)

- Did the participant have full understanding and no remaining questions with respect to the application of the VIBLOK Cream? (Yes / No)
- Did the participant have full understanding and no remaining questions with respect to the completion of the diary? (Yes / No)
- Did the participant have full understanding and no remaining questions regarding any other study procedure(s)? (Yes / No) • Medical History (general)
- Does the participant have hypertension? (No/Controlled / Uncontrolled)
- Does the participant diabetes? (No/ Type 1 / Type 2)
- Does the participant have cardiac disease? (Yes / No)
- Is the participant HIV positive? (Yes / No / Unknown)
- Does the participant have any known allergies? (No / Hay Fever, Dust Mites or Animal Dander / Contact Allergy / (Household) Chemicals / Perfume or Body care products / Latex / Other)
- Does the participant have a significant autoimmune disease? (No/ Multiple Scleroses / Myasthenia Gravis / Crohn Disease / Colitis Ulcerosa / Psoriasis / Vitiligo / Lupus Erythematosus / Rheumatoid arthritis /Other)
- Does the participant have any other for the study relevant medical condition? (Yes / No / Unknown)
- Have there been any changes in medical history since previous visit? (Yes / No)

The actual medical history status will be presented, i.e. the data from the previous visit including the changes reported at the respective visit.

- History of genital herpes
  - Did the participant experience HSV recurrence at Visit 1 since the screening visit? (No / Yes)
- Targeted Physical Exam
  - General
  - Heart rate (bpm)
  - Systolic and diastolic Blood pressure (mmHg)
  - Genital
  - Any new abnormalities in the inguinal and/or pubis area related to genital herpes? (Yes / No)
  - Any new abnormalities in the peri-anal area related to genital herpes? (Yes / No)
  - Any new abnormalities in the genital area related to genital herpes? (Yes / No)
  - Any new obvious discharge present in the genital, peri-anal, inguinal or pubis area? (Yes / No)
  - Any new other abnormalities in the genital, peri-anal, inguinal or pubis area, NOT related to genital herpes but relevant for the study (at the judgement of the investigator)? (Yes / No)
- The actual targeted Genital Exam will be presented, i.e. the data from the previous visit including the new abnormalities reported at the respective visit.
- Grooming Habits
  - Genital grooming habits (None / Shaving / Waxing / Other)
  - Frequency of performing these extra genital grooming habits (Daily / Weekly / Monthly / Other)

- Did participant change any genital grooming since the screening visit? (Yes / No) The actual grooming habits will be presented, i.e. the data from the previous visit including the changes reported at the respective visit.
- Medication vs Treatment
  - Are there any changes in medication, topical cream or any other product to alleviate genital herpes since previous visit? (Yes / No)
  - Anti HSV medication recorded on the participant's diary
  - Any anti HSV medication taken (Yes / No)
  - The percentage of days anti HSV medication taken in relation to the total number of days of participation.
- Review and collection of participant's diary
  - Did the participant complete the participant diary according procedure? (Yes / No, complete protocol deviation)
- Collection of participant swabs
  - Did the participant collect all required swabs according protocol? (Yes / No, complete protocol deviation)
  - Did the participant complete the swab log according protocol? (Yes / No, complete protocol deviation)
  - Did the participant complete the swab lesion log according protocol? (Yes / No, complete protocol deviation / Not applicable)
- Collection of participant questionnaire
  - Did the participant complete the participant questionnaire? (Yes / No, complete protocol deviation)
- Unscheduled FU information
  - Type of unscheduled follow-up (Phone call / In-Clinic visit)
  - Reason unscheduled follow-up (Genital Herpes outbreak / Other)
  - What type of treatment did the participant start to alleviate the outbreak of genital herpes? (No treatment / Prescription medication / Non Prescription medication / (Topical) cream / Any other treatment). More than one answer allowed.

In addition to tables giving group data for these variables, relevant individual participant data, and all concomitant medication for all individual participants enrolled (broken down by center) will be presented in by-participant tabular listings.

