8.1.2. Risks/ Adverse Events associated with VIBLOK cream

In addition to the events listed in the previous section, the additional adverse events listed below are specifically associated with the VIBLOK cream and its application. The lack of data associated with long term VIBLOK usage prevents predicting the incidence of these risks. Additional complications include, but may not be limited to:

- Toxic, hypersensitive or allergic reaction

- Epithelial sensitization

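### The SAP's 'actual' genital exam table carries past abnormalities forward, so at Visits 2 and 3 it shows cumulative occurrence since screening and not status at the visit or incidence on cream

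*SAP*

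**What the plan says.** The presentation rule appears twice in the SAP.

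- Section 3.4, for Visit 1: the exam shown is "the data from the screening visit including the new abnormalities reported at Visit 1".
- Section 3.6, on what follows, reads: "The actual targeted Genital Exam will be presented, i.e. the data from the previous visit including the new abnormalities reported at the respective visit".

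The follow-up genital items in section 3.6 are five Yes/No questions. Three concern findings attributed to herpes, by body area; one of them reads "Any new abnormalities in the genital area related to genital herpes? (Yes / No". A fourth asks about new discharge, with no attribution. The fifth covers other new abnormalities, "NOT related to genital herpes but relevant for the study (at the judgement of the investigator)? (Yes / No". None of the five offers an answer for a finding that has cleared.

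Medical history in the same section is handled differently: "The actual medical history status will be presented, i.e. the data from the previous visit including the changes reported at the respective visit". Updating by changes also applies to grooming habits. A change can be a resolution; a new abnormality cannot.

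Protocol 8.1.2 names the local risks of the cream, among them "Toxic, hypersensitive or allergic reaction" and epithelial sensitization. Under Protocol 5.2.3 the Visit 1 exam takes place before the first application.

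**The concern.** The genital exam is a clinician's view of the skin on which the cream is used. SAP 1.5 describes the study as single-arm and open-label, so change within participants over the visits is the natural reference for local tolerability. A table that cannot show healing serves that purpose poorly.

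Healing findings are to be expected in this population. Eligibility requires at least 3 recurrences in a year (Protocol 4.1), and antiviral therapy stops at least 7 days before Visit 1 (Protocol 5.2.2). Screening is less than 21 days before Visit 1, and Visit 3 is 26 to 31 days after it. The Visit 3 row can therefore repeat a finding made up to nearly 52 days earlier (21 + 31), before any cream was applied.

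Two misreadings are possible. A rising percentage could be taken as worsening on the cream when it is only accumulation. And a new finding in a participant whose Yes on that item predates the cream leaves the table unchanged.

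**Working it through.** The documents state no figure for genital exam findings, so there is none to reproduce. The check is first of the rule, then an illustration.

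**The rule.** For one Yes/No item, let S be the presented status and N the new-finding answer at a visit.

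- Visit 1 (SAP 3.4): S1 = screening Yes or N1.
- Visits 2 and 3 (SAP 3.6): S2 = S1 or N2; S3 = S2 or N3.

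So S3 is Yes if the item was Yes at any of the four exams. No term removes a finding. Within a participant, S can only stay level or rise, and if S1 is Yes, N2 and N3 have no effect on it.

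**Illustration.** These inputs are assumptions, not document figures: a chance p of a new finding at each of the four exams, a chance q that a finding has resolved by the next exam, independence between exams, and 46 participants (the planned number applying cream), all followed to Visit 3.

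- Presented at Visit 3 = 1 − (1 − p)^4.
- Actual at each visit = 1 − (1 − previous actual × (1 − q)) × (1 − p), starting from p at screening.

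For p = 5%, presented = 1 − 0.95^4 = 18.5%. Actual with q = 100% is 5.0% at every visit. With q = 50% it runs 5.0%, 7.4%, 8.5%, 9.0%.

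| p | Presented, Visit 1 | Presented, Visit 3 | Actual, Visit 3 (q = 100% to 50%) | Ratio at Visit 3 | Of 46 at Visit 3, presented vs actual |
|---|---|---|---|---|---|
| 5% | 9.8% | 18.5% | 5.0% to 9.0% | 3.7 to 2.1 | 8.5 vs 2.3 to 4.2 |
| 10% | 19.0% | 34.4% | 10.0% to 17.4% | 3.4 to 2.0 | 15.8 vs 4.6 to 8.0 |
| 20% | 36.0% | 59.0% | 20.0% to 32.5% | 3.0 to 1.8 | 27.2 vs 9.2 to 14.9 |

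**Against incidence on cream.** Any new finding at Visit 2 or 3 has probability 1 − (1 − p)^2. At p = 5% this is 9.75%, so the Visit 3 row (18.5%) is about twice the incidence on cream, and roughly half of it was already present at Visit 1.

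**How much is masked.** The share with a new finding at Visit 2 or 3 who were already Yes by Visit 1 is (1 − (1 − p)^2)^2. At p = 5% this is 0.0975 × 0.0975 = 0.95%, or 0.4 of 46. At p = 20% it is 0.36 × 0.36 = 13.0%, or 6.0 of 46. Under independence, masking is small when findings are rare; it grows if findings recur in the same participants.

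**The case against.** The strongest reply is that this is a descriptive table and that local reactions are reported elsewhere. Most of that stands.

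- **Adverse events.** Protocol 7.1 counts an untoward clinical sign as an adverse event and allows collection by investigator observation. Protocol 7.2 requires worsening of a pre-existing condition to be recorded. SAP 5.2.2 tabulates toxic and allergic reactions, relation to the device, HSV-2 complications, severity and outcome, including resolved. SAP 5.2.3 lists onset date, duration and causality. A reader might infer that new reactions are lost to the trial. They are not, provided they are reported as adverse events; they are only invisible in this table.
- **Mixing with herpes.** A reader might also infer that cream reactions are pooled with old herpes lesions. The items do not support that: a reaction judged unrelated to herpes has its own row. It can be merged there with an older non-herpes finding. Merging with herpes findings would need the reaction to be attributed to herpes, or to appear in the unattributed discharge row.
- **New items already displayed.** Section 3.6 lists the new-finding items among the displayed variables and plans by-participant listings. The carried-forward table may be meant as an addition. The SAP does not say so, and listings do not correct a mislabelled group percentage.
- **Unseen material.** The case report form is not supplied, and SAP 2.9 refers incomplete data to a separate plan. Resolution may be recorded there. As the SAP is written, it is not used.
- **Other exams.** The scheduled exam is not the only clinical view of the skin; Protocol 5.2.6 includes a genital exam at recurrence visits.

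**Conclusion.** The point holds for the table as specified. Following SAP 3.4 and 3.6 literally gives an ever-since-screening figure under a label that promises the actual exam. It is neither the state of the skin at the visit nor the incidence of findings on cream.

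Its size cannot be known from the documents. Under assumed new-finding rates of 5% to 20% per exam and 50% to 100% healing between visits, the Visit 3 figure overstates actual status about 1.8- to 3.7-fold. A larger multiple would need further assumptions, such as lower rates on cream than before it. The level-or-rise property holds within a participant; the group percentage can still fall as participants drop out and the denominator changes.

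The consequence is confined to a descriptive local-tolerability table. The SADE success criterion (SAP 5.2.1) and the swab analyses (SAP 4.2) do not use it.

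**What to change.** 1. In SAP 3.6, tabulate at Visit 2 and at Visit 3 the number and percentage of participants with a new abnormality as recorded at that visit, keeping the herpes-related, discharge and non-herpes rows separate. Add a row set for any new abnormality at Visit 2 or 3, that is, after first application.
2. In SAP 3.4, show screening findings and new findings at Visit 1 separately as pre-application baseline, and do not carry them into later visits. Changing section 3.6 alone would leave screening findings inside the Visit 1 baseline.
3. If a carried-forward table is kept, label it cumulative since screening and drop the word *actual*.

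The cost is SAP wording and revised table shells. The new-finding items are already collected, so no extra data are needed. The small downside is that the revised table gives incidence of new findings and not point prevalence; showing the state of the skin at each visit would need resolution to be recorded.
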